## **9. RESEARCH DESIGN AND METHODS**

**Overall Study Design.** The clinical trial will be registered under [www.clinicaltrials.gov](http://www.clinicaltrials.gov). Subjects between the ages of 18-65 who have a POTS diagnosis will be enrolled. Specifically, we will enroll patients who have hyperadrenergic POTS as confirmed by norepinephrine (NE) levels > 600 pg/ml. This is a 3-month study with a randomized double-blind placebo controlled cross over design. Subjects will be randomized into one of two groups (Ivabradine or placebo for one-month) then crossed over after a one-week washout period to the other group for one-month. Refer to Figure 1 below for details.

[figure not shown]

Figure 1. Randomized double-blind placebo-parallel group crossover trial with Ivabradine for patients with POTS.

**Study Visits.** There will be seven visits at the ACTRI and UCSD Cardiology clinics.

-Visit 1 is the pre-screening visit during which norepinephrine (NE) blood results will be obtained to confirm hyperadrenergic POTS diagnosis (NE> 600pg/ml). Orthostatic heart rate will be monitored. A urine pregnancy test will also be administered at this time. Post-menopausal women and women who are infertile will not be asked to take pregnancy test per PI discretion.

-At Visit 2, baseline lab work will be obtained to assess cardiometabolic health (CBC, CMP, TSH, T4, BNP). A tilt table test will be performed to determine baseline heart rate and QOL questionnaire (ShortForm36, SF36) will be completed. Orthostatic heart rate will be monitored. At this point, the patient will be randomized into the Ivabradine or placebo group for one month.

-At Visit 3, two-weeks into treatment, the patient will return to ACTRI for drug titration. Orthostatic heart rate will be monitored. If the patient fulfills criteria (see **Ivabradine Dosing** below), they will either increase, decrease, stop, or not change their Ivabradine dose.

-At Visit 4, one month after starting the current treatment, orthostatic heart rate monitoring, NE bloodwork, and QOL questionnaires will be completed. There will be a one-week wash-out period before the patient crosses over to the other group for one month.

-At Visit 5, the patient will return for orthostatic heart rate monitoring, NE bloodwork, and QOL questionnaires. A urine pregnancy test will be administered at this time. Post-menopausal women and women

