who are infertile will not be asked to take pregnancy test per PI discretion. The patient will be instructed to begin the secondary treatment (placebo or Ivabradine) for one month.

-At Visit 6, two-weeks into this treatment, the patient will return to ACTRI for drug titration. Orthostatic heart rate will be monitored. If the patient fulfills criteria (see **Ivabradine Dosing** below), they will either increase, decrease, stop, or not change their Ivabradine dose.

-At Visit 7, one month after starting the secondary treatment, the patient will return for orthostatic heart rate monitoring, NE bloodwork, and QOL questionnaires.

Blood samples will be saved and securely stored with the PI for future research analysis and purposes.

**Randomization.** Randomization refers to the order in which patients receive placebo or Ivabradine. If a patient receives Ivabradine first for one month, then he/she will be switched over to placebo for one month. If a patient receives placebo first for one month, then he/she will be switched over to Ivabradine for one month. There will be a one-week washout period prior to the cross-over. There will be 10 patients in each group.

**Ivabradine Dosing.** Ivabradine dose will initiate at 5mg twice daily (bid) and be increased to 7.5mg twice daily (bid) after 2 weeks if the heart rate is greater than 70 beats/min. If the heart rate is less than 70 beats/min there will no increase in dose. If the heart rate is less than 50 beats/min, or if the patient has symptoms of dizziness or lightheadedness, then Ivabradine will be stopped.

If patients have side effects and feel that cannot continue with Ivabradine we will decrease the dose from 7.5mg bid to 5mg bid (or if they are on 5mg bid to 2.5mg bid). After this dose reduction if the patient is still unable to tolerate Ivabradine, we will stop Ivabradine and withdraw patient from the study. If a patient is unable to tolerate Ivabradine (particularly prior to crossover period), he/she will be withdrawn. The starting dose and titration model is the same for the crossover treatment period as the initial month.

In our clinical experience using Ivabradine in patients with inappropriate sinus tachycardia (which are very similar to POTS patients in age and co-morbidities) we have not seen significant side effects that have caused patients to stop the drug. Refer to the uploaded Ivabradine Drug Information document for more details.

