**Statistical Analysis.** Continuous variables including mean heart rate, maximum heart rate, and quality of life scores will be summarized using descriptive statistics, including the number of observation (n) mean, standard deviation (SD), standard error (SE), median, the 1st (Q1) and 3rd (Q3) quartiles, minimum, and maximum values. The change in heart rate at one month from baseline will be compared by T-tests based on treatment status with placebo versus Ivabradine. Categorical variables will be compared by McNemar's test based on treatment status with placebo versus Ivabradine.

The study design will be adaptive and data analysis will be done in batches. The PI and others involved in data analysis will be blinded to who is the Ivabradine group and who is in the placebo group.

**Power Analysis.** Assuming a decrease in average heart rate of 10 beats/min is clinically significant (e.g. Decrease from 100 to 90; magnitude of effect 10%) with power 0.8 and standard deviation in heart rate is 7.5 beats/min, the estimated sample size is 18 patients. We will enroll 10 patients in each group to account for the 10% drop-out rate and to ensure the study is adequately powered. For sample size calculation, two-sided alpha level = 0.05 and two sample t-test are used.

**Drop-outs.** If any patient decides to withdraw from the study due to the intolerance of side-effects, we will try to obtain a tilt table test, orthostatic heart rate, QOL questionnaire, and blood tests at the time of drop-out.

**Documentation.** All patient related documentation will be stored at UCSD for future analysis as funding becomes available. To minimize the potential loss of confidentiality, patients will be assigned a unique number as their subject identifier code. The unique subject code will be used to label all study documents. The key that relates the code numbers to the individuals will be kept in a locked cabinet in the PI's office at the ACTRI.

All procedures mentioned above are research procedures and are not part of standard care.

Results may be used for diagnosis, treatment, and prevention of disease in patients.

**Incidental findings that result from the conduct of this study that require medical intervention for the subject will be noted by the PI or her project's medical research staff. They will refer the subject to his primary care physician. If the subject does not have a primary care physician one will be appointed for him or her.**

---

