## 10. HUMAN SUBJECTS

The study aims for 20 adult volunteers (18-65 years) to complete the study. Given the NE inclusion criteria, we will need to enroll at least 60 participants to have 20 participants pass the study screening criteria. With an expected drop-out of 10% after enrollment, this will provide 18 subjects for final analysis, which provides adequate power to detect a significant improvement in decreasing average heart rate at the 0.05 level (see power analysis, above). Participants will be screened and must meet inclusion and exclusion criteria before they are enrolled into the study. We will recruit patients from the cardiology and internal medicine clinics at UCSD Medical Center; in addition, we will utilize the bioinformatics report generated from EPIC and ResearchMatch to assist in recruitment. The main sites of the clinical testing will be conducted at the ACTRI and UCSD Cardiology clinics.

Inclusion/exclusion criteria are below:

1) Inclusion:

- a. Subjects aged 18-65
- b. Subjects must have POTS diagnosis (Hyperadrenergic Subtype with NE > 600pg/ml)
- c. Subjects with norepinephrine levels greater than 600 pg/ml
- d. Subjects with normal CBC, metabolic, and thyroid levels

2) Exclusion:

- a. Uncontrolled arrhythmias
- b. History of thyroid disease requiring dose titration of thyroid replacement medication(s) within the past 3 months (i.e. hypothyroidism on a stable dose of thyroid replacement therapy is not an exclusion)
- c. Drugs that interfere with Ivabradine (example: Cytochrome P450 drugs).
- d. Presentation of peripheral edema and discolored toes with peripheral autonomic neuropathy. Symptoms include: legs (reduced hair growth, cramps), toes (blue color), legs/feet (wounds, ulcers that do not heal), and muscles (numbness, heaviness).
- e. Subjects who have had a history of systemic illnesses (acute or chronic infectious); active and/or uncontrolled autoimmune/inflammatory disease, COPD, anemia, or diabetes.
- f. History of malignancy undergoing active treatment, except non-melanoma skin cancer.
- g. Uncontrolled psychiatric disorder (including history of hospitalization for psychiatric illness).
- h. Subjects with resting heart rate <60beats/min, atrial fibrillation, advanced AV blocks, sinus disease, and acute decompensated heart failure and severe hepatic impairment.
- i. Smokers or alcohol abuse.
- j. Pregnant or breastfeeding mothers.

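### The 80% power stated for 18 patients comes from a two-independent-group approximation that does not describe this crossover, and the plan does not say what its SD of 7.5 beats/min measures

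*Combined protocol and SAP*

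**What the plan says.** The Power Analysis paragraph of section 9 takes a 10 beats/min fall in average heart rate as clinically significant and continues: "with power 0.8 and standard deviation in heart rate is 7.5 beats/min, the estimated sample size is 18 patients". On the method it says: "For sample size calculation, two-sided alpha level = 0.05 and two sample t-test are used". It then enrols 10 per group, 20 in all, to allow for 10% drop-out. Section 10 relies on the result: "this will provide 18 subjects for final analysis, which provides adequate power to detect a significant improvement in decreasing average heart rate". Section 11 repeats the claim.

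The design is a two-period crossover in which only the order of treatments is randomised: "If a patient receives Ivabradine first for one month, then he/she will be switched over to placebo for one month", and the reverse for the other group.

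The Statistical Analysis paragraph says: "The change in heart rate at one month from baseline will be compared by T-tests based on treatment status with placebo versus Ivabradine". It does not say whether the t-test is paired. For categorical data it says: "Categorical variables will be compared by McNemar's test based on treatment status with placebo versus Ivabradine". McNemar's test is a within-patient method.

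On the baseline, the Visit 2 text says: "A tilt table test will be performed to determine baseline heart rate". Orthostatic heart rate is also taken at Visit 2 and at the one-month Visits 4 and 7. Heart rate is measured again after washout, before the second period: "At Visit 5, the patient will return for orthostatic heart rate monitoring, NE bloodwork, and QOL questionnaires".

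**The concern.** The calculation treats the trial as two separate groups of patients, but each patient contributes a result on both treatments. The quantity that governs power in such a trial is the SD of the within-patient difference between treatments. The plan gives neither that SD nor a correlation from which to derive it. The one SD it gives is described only as being in heart rate. It could be the SD of a single reading, of a change from baseline, or of a within-patient difference, and no source is cited.

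Sections 10 and 11 rest their claim of adequate power with 18 analysed patients on this calculation. If it does not apply, the plan has no valid statement of its power or of how much drop-out it can absorb.

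**Working it through.** **Inputs from section 9:** difference 10, SD 7.5, two-sided alpha 0.05, power 0.80, two-sample t-test, 18 patients. **Assumptions, not in the documents:** correlation r between any two visits, the same for all pairs, at 0, 0.3 and 0.5.

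**1. The plan's figure.** Normal approximation for two independent groups: n per group = 2 × (1.960 + 0.842)² × (7.5/10)² = 8.83, rounded up to 9, or 18 in total. The stated figure reproduces. Power by this approximation at 9 per group is 80.7%. Drop-out: 18/(1 − 0.10) = 20, which also reproduces.

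**2. The test the plan names.** Two-sample t-test, non-central t, non-centrality 10/(7.5 × √(2/n)):
- 9 per group, 16 df: 10/(7.5 × √(2/9)) = 2.83, power 75.7%.
- 10 per group, 18 df: 10/(7.5 × √(2/10)) = 2.98, power 80.5%.

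So 18 patients do not give 80% by the named test, even in a parallel-group trial.

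**3. The within-patient comparison.** Paired t-test, 18 completers, 17 df, non-centrality 10 × √18 / SD of the difference. Power is 80% when that SD is 14.27, or 14.22 if a period term takes one more degree of freedom.

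**4. If 7.5 is the SD of a single heart rate.**
- *Common baseline for both periods.* The baseline cancels within patient. SD of the difference = 7.5 × √(2(1 − r)).
- *Own-period baselines* (Visit 2 for period 1, Visit 5 for period 2). Four readings enter. SD of the difference = 7.5 × √(4(1 − r)) = 15 × √(1 − r).

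| r (assumed) | Common baseline: SD of difference | Power, 18 completers | Completers for 80% | Own-period baselines: SD of difference | Power, 18 completers | Completers for 80% |
|---|---|---|---|---|---|---|
| 0 | 10.61 | 96.4% | 11 | 15.00 | 76.0% | 20 |
| 0.3 | 8.87 | 99.4% | 9 | 12.55 | 89.0% | 15 |
| 0.5 | 7.50 | 99.96% | 7 | 10.61 | 96.4% | 11 |

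A period term lowers these powers by at most about 0.3 percentage points. With own-period baselines, 80% is reached when 15 × √(1 − r) = 14.27, that is at r of about 0.10.

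**5. The other readings of 7.5.** If it is the SD of a change from baseline, the SD of the difference is at most 7.5 × √2 = 10.61 for any non-negative correlation between a patient's two changes, so power is at least 96%. If it is the SD of the within-patient difference itself, power is 99.96%.

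**The case against.** The strongest reply is that nothing is miscalculated and little is at risk. The 18 follows from the stated inputs by a standard formula. The t-test needs only one more patient per group, and the plan enrols 20; sections 10 and 11 even say that 20 are meant to complete. On most readings the two-group calculation is conservative for a crossover. All of that stands, and it is why the point is a mismatch between design and calculation rather than an arithmetic slip. It does not rescue the power statement: sections 10 and 11 claim adequate power with 18 analysed, and no calculation in the plan supports that figure for this design.

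A second reply is that the plan never says the heart-rate t-test is paired, and the project title uses the words parallel group. That is correct. Pairing is inferred here from the crossover design and from McNemar's test, which is one reason the analysis text should say it.

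A reader might infer that, since the named test needs 20 analysed, any drop-out takes the trial below 80%. The documents do not support that. It holds only for two independent groups. Even an unpaired test on 18 crossover patients compares 18 values with 18; with a common Visit 2 baseline and 7.5 as the single-reading SD, its simulated power is 86%, 96% and >99% at r = 0, 0.3 and 0.5.

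A reader might equally infer from the common-baseline column that power is at least 96% and the matter is closed. The documents do not support that either. The heart rate called baseline at Visit 2 is a tilt-table value, while Visits 4 and 7 schedule only orthostatic heart rate. Visit 5 re-measures heart rate before period 2, so an own-period baseline is a live reading.

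**Conclusion.** The concern holds as a mismatch between design and calculation. The stated 80% at 18 patients is about 76% by the test the plan names, and that test describes a parallel-group trial, not this one. The power of the within-patient comparison cannot be fixed from the documents, because the SD of the within-patient difference, the baseline for period 2 and the meaning of 7.5 are all unstated.

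Underpowering is not shown. With 18 completers, power for 10 beats/min stays at or above 80% unless the SD of the within-patient difference exceeds about 14.3 beats/min. Among the cases worked above, only one falls short: 7.5 as the SD of a single reading, own-period baselines and no correlation between visits (76%).

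These figures assume a single analysis at two-sided 0.05. Section 9 also mentions an adaptive design with analysis in batches; its effect on alpha or power is not assessed here. The correction should be made, but it does not put the trial's size in doubt.

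**What to change.** Keep 20 randomised and 18 expected completers.

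1. In Statistical Analysis, state that the heart-rate comparison is within patient, by a paired t-test or a crossover analysis with a period term. This matches the design and the McNemar's test already planned.
2. State which heart-rate measure is used and which baseline applies in each period, taking baseline and one-month values from the same measure. Orthostatic heart rate is scheduled at Visits 2, 4, 5 and 7; a tilt-table test is scheduled only at Visit 2. Note that a common baseline cancels within patient, while own-period baselines raise the variance.
3. State what 7.5 beats/min measures and where it comes from. Then replace the two-sample statement with paired power for 18 completers. Until a within-patient SD or correlation is sourced, give the range, labelled as assumption: 96%, 99% and >99.9% with a common baseline, or 76%, 89% and 96% with own-period baselines, at r = 0, 0.3 and 0.5.
4. Refer sections 10 and 11 to the revised statement.

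If the two-sample calculation is kept, restate it as about 76% at 9 per group and label it a parallel-group figure.

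The cost is wording in sections 9, 10 and 11 and tracing the source of the SD. No patients, visits or measurements are added.

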## 10. HUMAN SUBJECTS

The study aims for 20 adult volunteers (18-65 years) to complete the study. Given the NE inclusion criteria, we will need to enroll at least 60 participants to have 20 participants pass the study screening criteria. With an expected drop-out of 10% after enrollment, this will provide 18 subjects for final analysis, which provides adequate power to detect a significant improvement in decreasing average heart rate at the 0.05 level (see power analysis, above). Participants will be screened and must meet inclusion and exclusion criteria before they are enrolled into the study. We will recruit patients from the cardiology and internal medicine clinics at UCSD Medical Center; in addition, we will utilize the bioinformatics report generated from EPIC and ResearchMatch to assist in recruitment. The main sites of the clinical testing will be conducted at the ACTRI and UCSD Cardiology clinics.

Inclusion/exclusion criteria are below:

1) Inclusion:

- a. Subjects aged 18-65
- b. Subjects must have POTS diagnosis (Hyperadrenergic Subtype with NE > 600pg/ml)
- c. Subjects with norepinephrine levels greater than 600 pg/ml
- d. Subjects with normal CBC, metabolic, and thyroid levels

2) Exclusion:

- a. Uncontrolled arrhythmias
- b. History of thyroid disease requiring dose titration of thyroid replacement medication(s) within the past 3 months (i.e. hypothyroidism on a stable dose of thyroid replacement therapy is not an exclusion)
- c. Drugs that interfere with Ivabradine (example: Cytochrome P450 drugs).
- d. Presentation of peripheral edema and discolored toes with peripheral autonomic neuropathy. Symptoms include: legs (reduced hair growth, cramps), toes (blue color), legs/feet (wounds, ulcers that do not heal), and muscles (numbness, heaviness).
- e. Subjects who have had a history of systemic illnesses (acute or chronic infectious); active and/or uncontrolled autoimmune/inflammatory disease, COPD, anemia, or diabetes.
- f. History of malignancy undergoing active treatment, except non-melanoma skin cancer.
- g. Uncontrolled psychiatric disorder (including history of hospitalization for psychiatric illness).
- h. Subjects with resting heart rate <60beats/min, atrial fibrillation, advanced AV blocks, sinus disease, and acute decompensated heart failure and severe hepatic impairment.
- i. Smokers or alcohol abuse.
- j. Pregnant or breastfeeding mothers.
- k. Woman of childbearing potential who are unwilling to use highly effective contraception during treatment and for an additional one month after discontinuing the study drug.

Highly effective contraceptive method (methods that can achieve a failure rate of less than 1% per year when used consistently and correctly) include:

- Combined hormonal (estrogen and progestogen) contraception associated with inhibition of ovulation (oral, intravaginal, transdermal)
- Progestogen - only hormonal contraception associated with inhibition of ovulation (oral, injectable, implantable)
- Intrauterine device (IUD)
- Intrauterine hormone-releasing system (IUS)
- Bilateral tubal occlusion
- Vasectomized partner
- Sexual abstinence
- Infertility

If the patient or patient's significant other is infertile, the PI may not require the patient to start other highly effective contraceptive methods in this case as they deem appropriate. The PI shall discuss with the patient and document the decision. The research team will document this in the patient's study file.

For female participants, the PI will administer a pregnancy test at the first visit to determine if patient will be excluded. Another pregnancy test will be administered prior to starting the crossover treatment.

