## 11. RECRUITMENT

We aim for 20 adult volunteers with confirmed hyperadrenergic POTS (NE > 600pg/ml) to complete the study. We will screen at least 60 patients in order to have 20 pass the screening phase and complete the study. With an expected drop-out of 10% after enrollment, this will provide 18 subjects for final analysis, which provides adequate power to detect a significant improvement in decreasing average heart rate at the 0.05 level (see power analysis, above). Participants will be screened and must meet inclusion and exclusion criteria before they are enrolled into the study. Additionally, the PI may ask a patient to return for a reevaluation of the baseline screening norepinephrine levels with a blood draw if she has reason to believe that the blood draw was done incorrectly or the results are inaccurate. This would be an additional in-person visit, but it does not increase the risk of the study.

We will recruit from the UCSD Medical Center cardiology and internal medicine clinics. Also, we will be utilizing ResearchMatch and the bioinformatics report from EPIC to help recruit patients who may qualify for our inclusion criteria. Each of these patients will be randomized into one of the two groups mentioned (Ivabradine or placebo).

We will be screening and recruiting patients through UCSD Medical Center clinics. We will also use ResearchMatch, which enables researchers to search for appropriate matches in non-identifiable volunteer profiles. We will be screening patients through EPIC, with the help of their bioinformatics department, for research subjects who might qualify for our criteria. EPIC Bioinformatics will help search for the following to generate a list of potential research subjects:

1. Patient's name, date of birth (DOB), and Medical Record Number (MRN)
2. Patient's primary care provider (PCP) name and contact information
3. POTS diagnosis
4. NE levels >600pg/dl
5. Ages 18-65
6. Exclusion:
  - a. History of thyroid disease requiring dose titration of thyroid replacement medication(s) within the past 3 months (i.e. hypothyroidism on a stable dose of thyroid replacement therapy is not an exclusion)
  - b. Drugs that interfere with Ivabradine (example: Cytochrome P450 drugs)
  - c. Presentation of peripheral edema and discolored toes with peripheral autonomic neuropathy. Symptoms include: legs (reduced hair growth, cramps), toes (blue color), legs/feet (wounds, ulcers that do not heal), and muscles (numbness, heaviness)

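### Sections 10 and 11 set a target of 20 completers, but the plan's own design randomises 20 and expects about 18 to finish, so the study team has two conflicting recruitment stopping points

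*Combined protocol and SAP*

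**What the plan says.** Four places in the combined protocol and SAP bear on the number of patients.

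- Section 9, Randomization: "There will be 10 patients in each group".
- Section 9, Power Analysis: the calculation returns 18 patients, and then "We will enroll 10 patients in each group to account for the 10% drop-out rate". The allowance for drop-out is what turns 18 into 20.
- Section 10: "The study aims for 20 adult volunteers (18-65 years) to complete the study". The next sentence says "we will need to enroll at least 60 participants to have 20 participants pass the study screening criteria", and the one after that "With an expected drop-out of 10% after enrollment, this will provide 18 subjects for final analysis".
- Section 11: the opening sentence again aims for 20 volunteers to finish. It continues: "We will screen at least 60 patients in order to have 20 pass the screening phase and complete the study". The sentence that follows makes the same 10% deduction and arrives at the same 18.

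The documents do not say whether a withdrawn patient is replaced. Section 9 (Drop-outs) says assessments will be attempted when a patient leaves because of side effects, but not how those data enter the analysis.

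**The concern.** The same 20 patients cannot all complete and also shrink to 18. Section 11 makes the clash plainest: the 20 who pass screening are the 20 who complete, and the next sentence takes 10% off them.

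At stake is when recruitment stops. A team working to the completion target would go on recruiting after each withdrawal; a team working to 10 per group would stop at 20 randomised. Withdrawals are foreseen, since section 9 provides for withdrawing patients who cannot tolerate the drug, so the question is likely to arise during the trial. If it is settled case by case, the final sample size and the balance of the two sequences depend on decisions made after withdrawals are known.

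The word for entering the trial adds to the confusion. Section 10 applies enrolment to the 60 people screened, section 11 calls the same 60 screened, and section 9 applies enrolment to the 20 randomised. A drop-out rate counted from enrolment then has no fixed base, although 18 makes sense only if the base is 20.

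**Working it through.** **Inputs, all from the documents.** Difference 10 beats/min, SD 7.5 beats/min, two-sided alpha 0.05, power 0.8, two-sample t-test, drop-out 10%, 10 per group (section 9); at least 60 screened for 20 passing (sections 10 and 11).

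**Step 1: reproduce the plan's figures.** By the normal approximation, n per group = 2 x (1.96 + 0.842)^2 x 7.5^2 / 10^2 = 8.83, rounded up to 9, so 18 in total (approximate power 80.7%). Inflating for drop-out, 18 / (1 - 0.10) = 20. Both the 18 and the 20 reproduce. In the sample-size section, 20 is the number randomised and 18 the number expected to remain.

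**Step 2: what 20 randomised deliver.** Expected completers = 20 x 0.9 = 18. If patients drop out independently, each with probability 0.10 (an assumption; the plan gives only the rate), the chance that all 20 complete is 0.9^20 = 0.122, about 12%. The chance that at least 18 complete is about 68%.

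**Step 3: what 20 completers require.** 20 / 0.9 = 22.2, so 23 randomised, or 24 for equal sequences. Under the same independence assumption, at least 20 complete with probability 81% from 23 and 91% from 24. At the plan's screening yield of 20/60 = 1/3, this means 23 x 3 = 69 to 24 x 3 = 72 screened.

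**Step 4: does the choice between 18 and 20 matter for power?** The plan names a two-sample t-test. With the exact (noncentral t) calculation and standardised difference 10/7.5 = 1.33:

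| Total | Per group | Power |
|---|---|---|
| 18 | 9 | 75.7% |
| 20 | 10 | 80.5% |

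Solving for 80% gives 9.89, so 10 per group. The 18 reaches 80% only under the normal approximation.

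If the crossover were analysed within patient, with an assumed correlation of 0 between periods, the SD of the difference is 7.5 x sqrt(2) = 10.6, and power is 96.4% with 18 patients and 97.9% with 20. A positive correlation raises both. The gap between 18 and 20 therefore matters mainly under the test that the sample size was based on.

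**The case against.** The strongest defence is that the documents largely settle the reading. Section 9 fixes 10 per group, the drop-out allowance sits inside the 20, and both recruitment sections end at 18 for analysis. The completion target is worded as an aim, and the stated arithmetic is correct. On this view it is loose wording with an evident meaning. That stands as far as the intended meaning goes: 20 randomised and about 18 completing is the better-supported reading. It does not remove the conflict, because the target of 20 completers appears three times in the two sections that govern recruitment.

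Three stronger readings are tempting, and the documents do not support them.

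- A reader might infer that replacing withdrawn patients would leave an analysed group made up only of people who tolerate the drug. No passage provides for replacement. That selection would come from withdrawing intolerant patients and then analysing completers only, with or without replacement. Section 9 also plans to attempt assessments at drop-out, and the plan does not settle whether those are analysed.
- A reader might infer that different sites would follow different rules. Section 15 describes a single-site study, so the ambiguity falls on one team.
- A reader might infer that 69 to 72 screened contradicts the plan. Both sections say at least 60, so it does not.

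**Conclusion.** The inconsistency is real and modest in size. The plan states 20 completers in sections 10 and 11, while its own design gives about 18. Meeting the stated target would take 3 to 4 more randomised patients than the 20 in section 9. The evidence favours 20 randomised with about 18 completing, so the completion wording should give way unless the sponsor intends otherwise.

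Settling on 18 should not be presented as preserving the stated power of 0.8. Under the named two-sample t-test it is about 76% with 9 per group.

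The completer figures rest on the plan's 10% drop-out, and the probabilities also assume independent drop-out. The power figures take the plan's SD and difference as given and assume the 18 split 9 and 9.

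**What to change.** 1. Use one set of figures in sections 9, 10 and 11: at least 60 screened, 20 randomised (10 per sequence), about 18 expected to complete.
2. Remove the three completion phrases: the one in the first sentence of section 10, and the two in the first two sentences of section 11 (the second reads "in order to have 20 pass the screening phase and complete the study").
3. In section 10, describe the 60 as screened rather than enrolled, matching section 11, and keep the qualifier that 60 is a minimum.
4. State that all randomised patients will be reported, including those withdrawn.
5. Where 18 is restated, give the power under the named test: about 76% at 9 per group, against 80.5% at 10 per group.
6. If the sponsor does intend 20 completers, state 23 randomised, or 24 for equal sequences, and that replacements are allocated within sequence.

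Items 1 to 5 change text only and add no patients or procedures; the price is an open statement that expected power under the named test is below 0.8. Item 6 would add 3 to 4 randomised patients and, at the plan's screening yield, bring screening to about 69 to 72. Either choice is best made before the first withdrawal.
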